	
 Section 7.3- Addition of the statement: "No human and/or animal tissues or their derivatives are found within the study product." Section 10.8- Addition of the statement: "The use of waivers is prohibited for deviating from the CIP". Updated section 7.2 and table 7 to add commercial DiamondTemp ablation system devices (unidirectional and bidirectional catheters, the RF Generator, Irrigation Pump, and its accessories) as they are market-released in the US. 	
procedure are not required for analysis of study endpoints/ objectives.
 
 Added per ISO 14155:2020 Requirement Added per ISO 14155:2020 Requirement As this is an indication expansion study in US and same procedural steps are applicable as commercial use of the Diamondtemp system for this study, Investigational centers in the US will utilize the commercially released DiamondTemp Ablation Catheters, RF Generator (and future commercially released generators), Irrigation pump and 			

DIAMOND-AF II Clinical Investigation Plan

Version H

Page 109 of 111

Medtronic
Form

Version	Summary of changes	Justification of changes	Potential impact of the change on performance, effectiveness, or safety or other endpoints	Identification of the affected study documents	Author(s)/Title
	
 Included “Investigator Role” within the Investigator Statement Section 8.4: Updated the “monitoring and auditing” responsibility language within per Medtronic template. Section 8.4: Added the statement, “Any data collection completed by Medtronic personnel will be clearly identified as such.” Section 7.6: Updated the product return instructions per Medtronic requirements. Section 13.3: Clarified the following comment: “All events will be analyzed by the Core Lab to determine arrhythmia recurrence.” 	
 its accessories for the remainder of this study. Updated language to match the updated Medtronic CIP Template Updated language to match the updated Medtronic CIP Template Updated language to match the updated Medtronic CIP Template Updated language to match the updated Medtronic CIP Template Updated language to match the updated Medtronic CIP Template 			
H	
 Changed enrollment from 400 to 376 	
 Version G of the protocol was not released to sites. Upon discussion with steering committee, it was determined to 	
None of the changes being made to the CIP Version H impact the performance of the device,
	
No study document affected
	
[name]

DIAMOND-AF II Clinical Investigation Plan

Version H

Page 110 of 111

Medtronic
Form

Version	Summary of changes	Justification of changes	Potential impact of the change on performance, effectiveness, or safety or other endpoints	Identification of the affected study documents	Author(s)/Title
	
 Deleted High Tech Med Consult (Czech Republic) as CRO from the from the synopsis Added the following to the Statement of Compliance: 
The study will comply with ISO 14155:2020 upon site activation on CIP version H, with noted exceptions outlined throughout the CIP and applicable study documents.
 
ISO14155:2020 exception for US; all activation related requirements will be conducted/collected in separate parts with exception of a formal SIV/visit report
 Deleted from 16.1 "The Investigator/institution guarantees direct access to original source documents by Sponsor personnel, their 	
request for the exact number of subjects that failed I/E criteria that were enrolled in the study Contract with CRO is terminated
 
 To clarify SIV documentation Duplicative language that is also captured under 16.1.2 Monitoring Procedures 	
principles of operation, and safety and efficacy of the study.
		

DIAMOND-AF II Clinical Investigation Plan

Version H

Page 111 of 111

Medtronic
Form

Version	Summary of changes	Justification of changes	Potential impact of the change on performance, effectiveness, or safety or other endpoints	Identification of the affected study documents	Author(s)/Title
	
designees, and appropriate regulatory authorities.”
 
• Minor changes throughout the protocol	
• Administrative changes/corrections

AFEQT	Atrial Fibrillation Effect on Quality of Life
AFL	Atrial Flutter
AT	Atrial Tachycardia
CEC	Clinical Events Committee
CIP	Clinical Investigation Plan
CTI	Cavotricuspid Isthmus
CSR	Clinical Study Report
CVA	Cerebral Vascular Accident
ECG	Electrocardiogram
ICF	Informed Consent Form
ITT	Intention-to-Treat
MedDRA	Medical Dictionary for Regulatory Activities
mITT	Modified Intention-to-Treat
OPC	Objective Performance Criterion
PeAF	Persistent Atrial Fibrillation
PP	Per Protocol
PT	Preferred Term
PV	Pulmonary Vein
PVI	Pulmonary Vein Isolation
RF	Radiofrequency
SAE	Serious Adverse Event
SAP	Statistical Analysis Plan
SOC	System Organ Class
TIA	Transient Ischemic Attack
WHO	World Health Organization

Introduction 3.

Atrial Fibrillation (AF) is the most common clinically significant cardiac arrhythmia and a major public health concern in the United States. AF is an abnormal heart rhythm that has been classified as

Revision 1

Page 4 of 18

recurrent when two or more episodes are detected. Episodes of AF that are continuous and sustained beyond 7 days but less than 12 months are classified as persistent AF (PeAF) according to the most recent 2017 HRS/EHRA Consensus Statement. Of all electrophysiological mechanisms responsible for AF, of significant interest are the pulmonary veins (PVs) which have been identified to play a critical role in triggering and maintaining AF.

The purpose of the Diamond-AF II study is to demonstrate the safety and effectiveness of the DiamondTemp Ablation System for the treatment of drug refractory, symptomatic persistent AF. The study will focus on pulmonary vein isolation (PVI) being the "cornerstone" of PeAF ablation but will allow physicians to consider additional ablation strategies per their standard ablation practice and within the recommendations of the study protocol.

This statistical analysis plan (SAP) outlines the data and procedures used for assessing the efficacy and safety endpoints of Protocol TP01071: A Prospective Clinical Evaluation of the DiamondTemp™ Ablation System for the Treatment of Persistent Atrial Fibrillation. This SAP has been developed prior to database lock to further describe the statistical methods and planned analyses of the study data to be included in the clinical study report (CSR).

Study Objectives 4.

Primary Safety Objective

To demonstrate that the primary safety event rate associated with the DiamondTemp ablation system is lower than the pre-specified Objective Performance Criterion (OPC).

Primary Effectiveness Objective

To demonstrate that the primary effectiveness rate associated with the DiamondTemp ablation system is higher than the pre-specified Objective Performance Criterion (OPC).

Secondary Objectives

- 1. To estimate the freedom from a composite of SAEs occurring within 30-days post-index ablation procedure as adjudicated by an independent CEC for relatedness to the procedure or device.
- 2. To estimate the freedom from documented AF/AFL/AT episodes during the effectiveness evaluation period lasting ≥ 30 seconds in duration by ECG monitoring.
- 3. To estimate the freedom from documented AF/AFL/AT episodes during the effectiveness evaluation period in the absence of class I and III anti-arrhythmic drug therapy.
- 4. To estimate the rate of acute procedural success.
- 5. To estimate the rate of single procedure success with freedom from AF/AFL/AT recurrence.
- 6. To estimate the rate of single procedure success with freedom from all primary effectiveness failure criteria.
- 7. To evaluate changes in QOL using the AFEQT Questionnaire.
- 8. To evaluate neurological changes measured using the NIH stroke scale.

Ancillary Objectives

1. To characterize procedural characteristics.

Diamond-AF II Statistical Analysis Plan Revision 1 Page 5 of 18 Medtronic

2. To characterize the number of re-hospitalizations due to Atrial Fibrillation recurrence during the effectiveness evaluation period.

5. Investigation Plan

The DIAMOND-AF II Study is a prospective, non-randomized (single-group assignment) trial being performed at multiple centers in the United States, Canada and Europe to evaluate the safety and effectiveness of the DiamondTemp Ablation System for the treatment of patients with persistent atrial fibrillation.

This study will enroll up to 376 subjects diagnosed with persistent AF at up to 30 investigational sites in the US, Canada and Europe. Investigational sites will have a principal investigator (PI) that is responsible for the conduct of a research study as well as sub-investigators. It is anticipated that approximately 50% of the subjects will be enrolled at centers within the United States. The maximum number of enrollments per site should not exceed 20%. Subjects will be followed for a minimum of 12 months post index ablation procedure.

6. Determination of Sample Size

For the primary safety endpoint, a sample size of 269 achieves 81% power to detect a difference of at least -4.5% using an Objective Performance Criterion (OPC) of 11.5% and a one-sided target level of significance of 0.025. Reference Section 7.9.1 for relevant statistical hypotheses.

Similarly, for the primary effectiveness endpoint, a sample size of 274 yields 86% power to detect a difference of 9% using an OPC of 40% and a one-sided target level of significance of 0.025. Reference Section 7.9.2 for relevant statistical hypotheses.

Assuming a drop-out rate of 12%, as well as accounting for eligibility/screen failures, the enrollment goal of up to 376 subjects should be sufficient.

7. Statistical Methods

7.1 Study Subjects

7.1.1 Disposition of Subjects

Subject disposition will be illustrated by a study flow diagram, detailing subject enrollment, treatment, follow-up, and attrition.

[figure not shown]
Inclusion and Exclusion criteria violations will be summarized, as well as follow-up compliance and reasons for premature study discontinuations. The number of subjects included in each of the analysis populations (as defined in Section 7.1.3) will be summarized.

7.1.2 Clinical Investigation Plan (CIP) Deviations

Protocol deviations will be summarized in the clinical study report by coded category. The number of deviations per category, and the number and percentage of subjects with a deviation in each category will be reported. A listing showing the protocol deviation details will also be provided.

Revision 1

Page 6 of 18

7.1.3 Analysis Populations

Three analysis populations are defined for this study:

Intention-to-Treat Population

The Intention-to-Treat (ITT) population will be comprised of all subjects who sign Informed Consent Form (ICF) and attempt study treatment (i.e., catheter inserted into vasculature).

Modified Intention-to-Treat Population

The modified ITT (mITT) population will be a subset of the ITT population and comprised of all ITT subjects who meet eligibility criteria.

The primary effectiveness and safety analysis will be conducted using this mITT population.

Per Protocol Population

The Per Protocol (PP) population will be a subset of the mITT population and comprised of all mITT subjects who do not have any major protocol deviations (i.e., eligibility criteria violations, or ablation treatment with a non-study catheter for the index procedure or during blanking period).

All study objectives will be analyzed using the mITT population. Additionally, sensitivity analyses of the primary safety and effectiveness objectives will be performed using the ITT and PP populations.

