If at any time during the ablation procedure the Investigator is unable to continue the ablation with the investigational catheter (other than when ablating an RA flutter line), the Investigator may consider the case a procedural failure and complete the case with a device determined best for the subject. The point at which failure was determined as well as the rationale must be documented.

After removal from the subject, the investigational catheter should be inspected, and if any abnormalities such as char or coagulum formation are noted on the catheter, it must be documented. All adverse experiences with the investigational device during the ablation procedure must be promptly reported to the Sponsor and documented on the CRF.

Post-Procedure Anticoagulation

Investigators may use protamine to reverse the intravenous heparin used during the procedure.

- Subjects must be anticoagulated for a minimum of 60 days post index ablation procedure. It is up to the Investigator's discretion which drug is best suited for the subject.
- If anticoagulation was discontinued prior to and during the ablation procedure, anticoagulation should be resumed within 24 hours post-procedure to achieve a therapeutic anticoagulation level.
- It is recommended that Investigators follow the anticoagulation guidelines set forth in the 2017 HRS Expert Consensus Statement on Catheter and Surgical Ablation of AF^[10], regardless of the apparent success or failure of the AF ablation procedure.
- Additionally, the Investigator's decision regarding continuation of systemic anticoagulation more than 60 days post ablation should be based on the subject's stroke risk profile (CHA₂DS₂-VASc score ≥ 2 in men and ≥ 3 in women, prior stroke or TIA and/or age ≥ 75 years) and not on the perceived success or failure of the ablation procedure.

Post-Procedure AADs

- If AADs are restarted following the ablation procedure, it is recommended to maintain subjects on a drug regimen for a duration of 2 to 4 weeks to address symptoms or early recurrences of AF, AFL or AT during the post-ablation healing and stabilization phase.
- If AADs are restarted for clinical reasons during the blanking period but not later than the 3-month follow-up visit, it is recommended that subjects are maintained under the same AAD regimen throughout the effectiveness period (12-month follow-up). During the effectiveness evaluation period, physicians may discontinue an AAD, but may not add a new class or escalate an AAD.

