14.1 Analysis Populations

Three analysis populations are defined in this study:

- The Intent-to-Treat (ITT) population will be comprised of all subjects who sign ICF and attempt study treatment (i.e. catheter inserted into vasculature).
- The modified ITT (mITT) population will be a subset of the ITT population and comprised of all ITT subjects who meet eligibility criteria.
- The Per-Protocol population will be a subset of the mITT population and comprised of all mITT subjects who do not have any major protocol violations (i.e. eligibility criteria violations, or ablation treatment with a non-study catheter for the index procedure or during blanking period).

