7.9.2 Primary Effectiveness Objective

Primary Effectiveness Objective

To demonstrate that the primary effectiveness rate associated with the DiamondTemp ablation system is higher than the pre-specified Objective Performance Criterion (OPC).

Hypothesis

Revision 1

Page 11 of 18

 H_0 : $P \leq P_0$

 $H_1: P > P_0$

where $P_0 = 40\%$ (Effectiveness OPC), and higher effectiveness rates are better.

Endpoint Definition and Derivation

The primary effectiveness endpoint is defined as freedom from documented Atrial Fibrillation (AF), Atrial Flutter* (AFL) and Atrial Tachycardia (AT) episodes following the blanking period (3-month followup post-ablation procedure) through the end of the effectiveness evaluation period (12-month followup post-ablation procedure).

An effectiveness failure is defined by any of the following events:

- Inability to electrically isolate all accessible targeted pulmonary veins during the ablation procedure.
- Documented episodes of AF, AFL or AT lasting ≥ 30 seconds in duration as evidenced by electrocardiographic data during the effectiveness evaluation period.
- DC cardioversion for AF, AFL or AT during the effectiveness evaluation period.
- A repeat ablation procedure to treat AF, AFL or AT during the effectiveness evaluation period.
- Use of a new or previously failed anti-arrhythmic drug (AAD) at a dose greater than the highest ineffective dose for AF during the effectiveness evaluation period.
- Use of a non-study device for ablation of any AF targets during the index or repeat ablation procedure during the blanking period.
- More than one (1) repeat ablation procedure during the blanking period.

The blanking period for a subject starts on the date of the index ablation procedure (day 0) and ends on day 90 post index ablation.

The effectiveness evaluation period for a subject starts on day 91 post index ablation and ends on the study exit date or day 410 post index ablation (i.e., close of the 12-month visit window), whichever is earlier.

If a primary effectiveness failure event occurs post day 365 and within the effectiveness evaluation period, the date of the event will be set to day 365 so that these events will be accounted for in the 12month Kaplan-Meier estimate of the primary effectiveness endpoint.

Performance Requirements

The null hypothesis will be rejected if the one-sided 97.5% lower confidence bound of the primary effectiveness rate is greater than 40%.

[figure not shown]

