The main analysis of the primary effectiveness objective will be based on the mITT population, which includes all subjects who sign informed consent, meet eligibility criteria and attempt study treatment (i.e., catheter inserted into vasculature). Additionally, sensitivity analysis for the primary effectiveness objective will be conducted on the Per-Protocol population, which includes all mITT subjects who do not have any major protocol violations (i.e., eligibility criteria violations, or ablation treatment with a nonstudy catheter), and the ITT population, which includes all subjects who sign informed consent and attempt study treatment.

[figure not shown]

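### The only Per-Protocol exclusion that removes anyone overlaps a primary effectiveness failure criterion, so the Per-Protocol effectiveness analysis leans upward relative to mITT

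*SAP*

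**What the plan says.** Both documents build the three populations in the same way (Protocol 14.1, SAP 7.1.3). ITT is everyone who consented and had the catheter inserted. mITT is "comprised of all ITT subjects who meet eligibility criteria". PP is mITT without major deviations, and an *i.e.* list gives those deviations as "eligibility criteria violations, or ablation treatment with a non-study catheter for the index procedure or during blanking period". SAP 7.1.3 states the purpose: "sensitivity analyses of the primary safety and effectiveness objectives will be performed using the ITT and PP populations".

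The failure criteria in SAP 7.9.2 include "Use of a non-study device for ablation of any AF targets during the index or repeat ablation procedure during the blanking period". A footnote in the same section says that CTI-dependent flutter, or its ablation, is not a failure. Protocol 10.6.2 lets an investigator who cannot continue with the study catheter call the case a procedural failure and finish with another device, "other than when ablating an RA flutter line".

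Where SAP 7.9.2 restates PP for the effectiveness analysis, the time limit is missing: "eligibility criteria violations, or ablation treatment with a nonstudy catheter". Another failure criterion in that section is "A repeat ablation procedure to treat AF, AFL or AT during the effectiveness evaluation period", and Protocol 10.7.3 permits commercial devices for repeat procedures after blanking.

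**The concern.** A sensitivity analysis on a different population should be able to disagree with the main analysis in either direction. Here the exclusion rule and the endpoint share a component. Removing subjects because they met a failure criterion conditions on the outcome, so agreement between PP and mITT says little about robustness. The subjects removed include those whose procedure could not be completed with the study catheter, which is part of the performance that the trial measures. What is at stake is how the PP effectiveness result is read, most of all when the mITT result is close to the 40% goal.

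**Working it through.** **The sets**

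1. PP = mITT minus (a) eligibility violations and (b) a non-study catheter at index or in blanking. The *i.e.* makes the list exhaustive as written.
2. Every mITT subject meets the eligibility criteria, so (a) is empty.
3. Item (b) and the failure criterion cover the same kind of device and the same window (index, or a repeat procedure in blanking). The criterion is limited to AF targets; item (b) is not.
4. Subjects removed under (b) are therefore of two kinds: those with an AF target ablated, all failures by definition, and those with only non-AF targets ablated, who may be successes or failures.

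**Direction**

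Without censoring, removing k failures changes the rate from x/n to x/(n−k), which is always higher. Under Kaplan-Meier with censoring the estimate also cannot fall. In 3000 simulated data sets with random censoring, removing one failure never lowered it.

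If s of the k removed subjects are successes, PP is (x−s)/(n−k). This is below x/n only when s/k exceeds x/n. With x/n = 134/274 = 48.9% and k = 10:

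- s = 4: 130/264 = 49.2%, still above mITT
- s = 5: 129/264 = 48.86%, just below mITT (48.91%)

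**Inputs for size**

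- From SAP 6 and 7.9.2: N = 274, goal 40%, design difference 9 points (so 49%), one-sided 0.025, log-log bound, stated power 86%.
- Assumed: k, which the documents do not give. A range of 3 to 27 is used, about 1% to 10% of 274. All k are taken to be failures and there is no censoring.

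**The plan's own figure**

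Power = Φ[(0.09 − 1.96·√(0.4·0.6/274)) / √(0.49·0.51/274)] = Φ[(0.09 − 0.0580)/0.0302] = 85.5%, which agrees with the stated 86%. With the log-log bound and no censoring, success needs at least 127/274 and power is 82.6%.

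**Lower bounds**

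With S = x/n, the standard error on the log-log scale is √[(1−S)/(nS)] / |ln S|. The lower bound is exp{−exp[ln(−ln S) + 1.96·SE]}.

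Worked case, 125/274: S = 0.4562, −ln S = 0.7848, SE = 0.0660/0.7848 = 0.0840. The bound is exp{−exp[−0.2423 + 0.1647]} = 39.6%.

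| mITT (bound) | k removed | PP (bound) | 40% goal |
|---|---|---|---|
| 134/274 = 48.9% (42.9%) | 3 | 134/271 = 49.4% (43.4%) | met in both |
| 134/274 | 10 | 134/264 = 50.8% (44.6%) | met in both |
| 134/274 | 27 | 134/247 = 54.3% (47.8%) | met in both |
| 125/274 = 45.6% (39.6%) | 3 | 125/271 = 46.1% (40.1%) | missed, then met |
| 122/274 = 44.5% (38.6%) | 10 | 122/264 = 46.2% (40.1%) | missed, then met |

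**The case against.** The strongest reply is that nothing important rests on PP. Study success is decided on mITT, where these subjects count as failures, and they remain failures in the ITT sensitivity analysis. Nothing in the documents lets a PP result rescue a missed mITT goal. That stands, and it limits the weight of the point.

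A reader might infer that the rule hides cases that the study catheter could not complete. The documents do not support that. SAP 7.9.2 reports the number and percentage of subjects meeting each failure component, SAP 7.1.2 tabulates and lists deviations, SAP 7.1.1 gives the size of each population, and Protocol 10.6.2 requires the point of failure and the reason to be documented.

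A reader might also infer that PP must agree with or beat mITT whatever the data. That is too strong. Item (b) has no AF-target limit, Protocol 10.6.2 allows prophylactic CTI lines and ablation of spontaneously occurring atrial arrhythmias, and the documents do not define an AF target. PP can therefore remove some successes.

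Two further replies are fair. The crossings of 40% come from success counts chosen just below the 127 needed; at the design rate the conclusion does not change. And performance in subjects treated only with the study catheter is an ordinary per-protocol question. For safety it remains a useful one, because catheter use is not a safety event. For effectiveness it does not work as a robustness check, because the answer is partly built into the endpoint.

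**Conclusion.** The point holds for the PP effectiveness analysis only. The eligibility clause removes nobody, and the remaining exclusion removes failures by definition whenever an AF target was ablated. PP is thus biased upward relative to mITT unless the share of successes among those removed exceeds the mITT success rate.

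The size depends on a count that the documents do not give. Near the design rate, 3 to 27 removed failures lift the lower bound from 42.9% to between 43.4% and 47.8%, with no change in conclusion. In a near miss, as few as 3 can carry the PP bound past 40%. These figures assume that every removed subject is a failure and ignore censoring, including the planned 12% drop-out.

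Since neither the mITT decision nor the ITT analysis is affected, this is a minor to moderate point. It is worth correcting before database lock because the analysis is labelled a sensitivity analysis.

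**What to change.** In SAP 7.1.3 and 7.9.2 and Protocol 14.1:

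1. For the effectiveness PP analysis, keep subjects who had an AF target ablated with a non-study device at index or in blanking, and count them as failures. The exclusion can stay for the safety PP analysis.
2. Delete the eligibility clause from the PP definition.
3. Use one time window and one AF-target wording in the PP definition, its restatements and the failure criterion. As restated in SAP 7.9.2 without a time limit, PP would also drop post-blanking repeat ablations done with a commercial catheter, which are failures when done for AF, AFL or AT.
4. If the effectiveness PP analysis is to exclude anyone, use only recorded deviations that are not endpoint components. Antiarrhythmic drug use after day 90 does not qualify, because it can itself be a failure.

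The cost is SAP and Protocol wording and one re-derived population flag. Under Protocol 14 and SAP 7.11 an amendment is needed only if a principal feature changes; otherwise the change is described in the study report. The downside is that the PP estimate may be less favourable and PP may nearly coincide with mITT for effectiveness.
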